C.4.1 Study Design. This is a pragmatic, cluster randomized comparative effectiveness trial. Given the complexity of systems and processes needed to implement SMAs, and the possibility of contamination effects, randomization will be clustered at the practice level using covariate constrained randomization.⁵⁵⁻⁵⁷ Twenty-two practices will be randomly assigned to either standardized or patient-driven diabetes SMAs (10 per condition). During the 24-month implementation period, each practice will conduct SMAs with around 8 cohorts of 8 to 10 patients each (ultimately yielding up to 72 patients per practice). The initial plan is that cohorts of adult patients with T2DM will progress through 6 weekly SMA sessions, and a new cohort will begin every 3 months, but practices can choose their own timeline. A mixed-methods evaluation will include quantitative (practice and patient-level surveys, electronic health records (EHR), and participation and intervention fidelity tracking data) and qualitative (practice and patient interviews, observation) components.

Sample Size and Power Calculations: Previous power calculations used 1,440 total patients, which is not feasible given recruitment challenges by practices. We are expecting N (total) = 22 clinics, 1,000 patients (11 clinics and 500 patients

PRINCIPAL INVESTIGATOR (LAST, FIRST, MIDDLE): [name]

per condition), allowing for ~15-20% attrition (leaving 400 patients per arm). However, we are estimating power based on 20 practices and provide a possible range of potential power to detect main effects. We estimated the minimum effect sizes detectable for different power calculations for various numbers of practices and patient sample sizes and intraclass correlations (ICC; see table below), with effect sizes of approximately .29 to .35 for intent-to-treat analyses of primary outcomes with a type-1 error rate of .05. Power for planned subgroup analyses for patient characteristics (e.g., mental illness, health literacy) is also shown. An effective sample size of 67 per group is required to detect a medium linear trend effect between groups (increasing from 0 to .5SD) using general linear mixed models with random slopes and intercepts.⁵⁸

| Practices per arm: N | Patients per practice: N | With 15-20% attrition: N | ICC | Effective sample size | Detectable difference (effect size) | Power |

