randomization procedure.⁸⁸ **Covariates (to adjust for potential confounding) and potential moderators will include the following:** mode of delivery of SMA (in-person vs. telehealth), age, gender, race/ethnicity, comorbidity index, insulin dependence, baseline diabetes distress, health literacy, and mental illness. Recent literature on cluster randomized trials notes that imbalance in covariates is more of a problem than for individually randomized trials, and covariates should be included to improve precision and should be selected prior to analysis.^{55,88,89} In the event normality assumptions are not met, we will use transformations to normalize distributions, ordinal or Poisson regression where appropriate, and/or the appropriate link function (e.g. logit link for dichotomized measures).⁹⁰⁻⁹² We will employ intent to treat analyses using general (generalized) linear mixed models (GLMMs) to incorporate data structures that are both hierarchical and longitudinal.^{91,93-97} Hypothesis tests will be two-sided with $\alpha = .05$ or p values reported. Goodness of fit statistics and model fitting diagnostics will be used to assess for influential points, outliers, overdispersion and heteroscedasticity and to evaluate alternative model specifications.⁹⁰ All statistical analyses will be performed using SAS version 9.4 (SAS Institute Inc., Cary, N.C.).

Missing Data (MD-2). Prior to beginning analyses described below to address study hypotheses, we will examine the data carefully to determine whether patterns of missing are ignorable (MCAR or MAR) or non-ignorable (MNAR).⁹⁸⁻¹⁰¹ If so, we will employ likelihood-based methods that utilize all available data (MD-4), adjusting for covariates that are associated with missingness (MD-3). If missingness is non-ignorable we will employ pattern mixture models.¹⁰² Sensitivity analyses will be carried out using multiple imputation approaches (MD-5).

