Quantitative analysis plan. The following analyses will be carried out by [name] and the quantitative analyst. In recent literature on cluster randomized trials, general (or generalized) linear mixed models, adjusted for covariates are recommended for analysis of cluster randomized trials,^{89,103} even after using such procedures as constrained randomization.⁵⁴ Likelihood based models using all available data are the preferred method for analyzing longitudinal data with dropout under MAR conditions.¹⁰⁴⁻¹⁰⁷ This will be our primary analysis; however, we will examine change scores as outcomes, adjusting for baseline, in sensitivity analyses.

To test hypothesis I (comparing patient-centered outcomes): The outcomes for these analyses will be patients' scores on each of these measures at baseline and follow-up (1st and last session). The structure of the data is hierarchical (patients nested within practices) and repeated measures on patients over time. In the basic mixed effects model shown below, Y_{tij} is the score for patient i at time t (baseline: time=0, or follow-up: time=1) in practice j . Intervention is an indicator variable: 0=standard SMA, 1=patient-driven SMA. Covariates will be included in all models but are not shown here for ease of understanding.

$$Y_{tij} = \gamma_{000} + \gamma_{010}(\text{intervention}) + \gamma_{100}(\text{time}) + \gamma_{110}(\text{intervention} \times \text{time}) + u_{00j} + r_{0ij} + \varepsilon_{tij}$$

where γ_{000} represents the initial status for standard SMA; γ_{010} represents the baseline difference between the patient driven SMA practices and standard SMA practices (should be close to 0); γ_{100} is the pre-post change in scores for the standard SMA practices; γ_{110} is the *difference* in pre-post change (i.e. difference in difference) for standard vs. patient-driven SMA practices. r_{tij} is a patient random effect and u_{00j} is a practice random effect, independent of r_{tij} and assumed to have a bivariate normal distribution over practices; ε_{tij} is residual variance. Thus, the intervention effect of patient-driven vs standard SMAs can be tested as $H_0: \gamma_{110}=0$ vs $H_1: \gamma_{110} \neq 0$.

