In the model above we use practice level random effects. However, it is possible that groups (within practices) are a greater source of variation than practices per se. Therefore, we will estimate variance components for groups within practices and retain both random effects if there is sufficient variability. If it is not possible to retain both group and practice random effects, we will test each separately and examine model fit and variance components to determine which to retain.

To test hypothesis II (comparing clinical outcomes): Outcomes for these analyses will be obtained from EHR data covering 9 months' post-baseline for each patient. The baseline measure for each clinical outcome will be defined as the last recorded value prior to enrollment in the study. All subsequent clinical measures through 9 months after enrollment will be used in analysis. Analytic approaches will be similar to those described for hypothesis 1, with time will be coded

PRINCIPAL INVESTIGATOR (LAST, FIRST, MIDDLE): [name]

as time since baseline. Random coefficient growth curve models will be used to determine whether trajectories for patients in standard SMA practices differ from patients in patient-driven SMA practices (time x arm interaction term in mixed model notation).

Hypothesis III. Compared to standardized diabetes SMAs, practices using patient-driven diabetes SMAs will exhibit greater improvements in quality and team-based care, as measured by the Relational Coordination Survey and the Assessment of Chronic Illness Care.

To test ***hypothesis III (comparing patient reach and engagement)***. The outcomes for these analyses will be 1) acceptance of services (Y/N), and 2) number of SMA sessions attended. General or generalized linear mixed effects models (depending on distribution of outcomes variable) with a practice random effect will be used for analysis. In addition to including covariates as described above, we will test whether mental illness is a moderator of intervention effectiveness. This will involve including a main effect for mental illness, along with an arm x mental illness interaction term (mixed model notation).

To test ***hypothesis IV (comparing practice quality and team based care)***: Outcomes for this analysis will be scores on the relational coordination survey and the ACIC at baseline, 9, and 24 months. Analytic approaches will be similar to those described for hypotheses I and II.

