Heterogeneity of treatment effects (HTE) (HT-2). It is not known at this time whether patient-driven SMAs will benefit certain patients more than others. Thus, in addition to the analyses described above, we will conduct exploratory analyses to test for potential effect modification (moderator of intervention effectiveness) by selected patient characteristics (HT-1). While this study may be powered to detect effect modification with large effect sizes, the planned sample size of 1000 enrolled will allow only for testing effect modification of patient characteristics representing subgroups of an average of 10 patients per practice with that characteristic. For example, to do a subgroup analysis of patients with mental illness, we would need an average of 10 patients with mental illness per practice to test this effect. This analysis is described just above for analysis of hypothesis IV with mental illness as a potential moderator; mental illness comorbidity is our primary target for HTE analyses and will be examined for every hypothesis above. Additional sub-populations of interest are defined by gender, Hispanic ethnicity, and health literacy; existing evidence suggests possible differential participation and effectiveness for these groups.^{29,108,109} The general hypothesis for these moderator analyses is as follows: The effects of the patient-driven vs standardized SMAs on diabetes distress (and other primary and secondary outcomes) will differ for patients with mental illness compared to patients without mental illness (male vs. female, Hispanic ethnicity vs not, high vs. low health literacy, food security, cohort conducted in English or Spanish, virtual vs. in-person, insulin dependence). To assess for possible heterogeneity of treatment effects by mode of delivery (effect modification, moderator) additional analyses will be performed including the appropriate two and three-way interactions between treatment arm and mode: arm x modality interaction for single outcomes, arm x time x modality along with relevant two-way interactions for longitudinal analyses. Additionally, sensitivity analyses will be performed to further explore delivery mode. Additionally, we will examine variability between SMA groups separately for standard and patient-driven arms to determine if the group itself (especially in the patient-driven arm) is an important contributor to differences in outcomes.

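### The printed primary DDS-17 model has no practice-by-time random effect, so its test of the arm difference in change ignores practice-to-practice variation in change, and equation and text conflict

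*Combined protocol and SAP*

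**What the plan says.** All references are to the combined protocol and SAP.

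- **Design (C.4.1).** Practices are the unit of randomisation. The current plan is 22 practices (11 per arm), with power estimated on 20.
- **Primary model (C4.4.2d.1, hypothesis I).** DDS-17 is measured at the first and last session. The equation has fixed effects for arm, time and arm x time, and three random terms: practice intercept u_00j, patient intercept r_0ij and residual. The text then says "Thus, the intervention effect of patient-driven vs standard SMAs can be tested as" gamma_110 = 0. Only covariates are said to be left out of the display.
- **Text under the equation.** The practice effect is "assumed to have a bivariate normal distribution over practices". The same sentence labels the patient effect r_tij, where the equation has r_0ij.
- **Sensitivity analysis.** "we will examine change scores as outcomes, adjusting for baseline, in sensitivity analyses", with no random effects stated.
- **Groups (next paragraph).** Practice and group effects are both kept if there is sufficient variability. If both cannot be kept, "we will test each separately and examine model fit and variance components to determine which to retain".
- **Power table (C.4.1).** Effective sample sizes of 193, 140, 181 and 134 per arm at ICCs of 3% and 5%, with detectable effects of .29 to .35 and power above 80%. Whether the ICC refers to scores or to change is not stated.

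**The concern.** The parameter of interest is a difference in pre-post change. Practice teams deliver the intervention between the two measurements, so practices may differ in how much their patients change for reasons unrelated to arm. That variation is the relevant error for a practice-randomised comparison. A random intercept captures only differences in level that persist over time, and those cancel from change.

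If the equation is fitted as printed, patients' changes are treated as independent within practice. Any real practice variation in change then makes the primary confidence interval too narrow and the p-value too small. If a practice slope was intended, the primary model is not the one written, and the analyst would have to settle the structure with the data in hand.

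**Working it through.** **1. Reproducing the power table.** Effective n = k*m / [1 + (m-1)*ICC], with k = 10 practices per arm. Detectable effect = (1.96 + 0.84)*sqrt(2/effective n).

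| m | ICC | Design effect | Effective n | Detectable effect | Printed |
|---|---|---|---|---|---|
| 44.5 | 3% | 2.305 | 193.1 | 0.285 | 193 / .29 |
| 44.5 | 5% | 3.175 | 140.2 | 0.335 | 140 / .34 |
| 38.5 | 3% | 2.125 | 181.2 | 0.294 | 181 / .30 |
| 38.5 | 5% | 2.875 | 133.9 | 0.342 | 134 / .35 |

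The table is internally correct (81-82% power at the printed effects). It charges the arm comparison for practice clustering.

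**2. What the printed test carries.** Under the printed model a patient's change is gamma_100 + gamma_110*arm + (residual at follow-up - residual at baseline). Both u_00j and r_0ij are gone. With complete balanced pairs the test is therefore a two-sample test of patient changes that ignores practice. REML fits to four simulated data sets containing a practice slope confirmed this: z and standard error matched that two-sample test to four decimals (for example z = 2.1770 by both, SE 0.0683 by both).

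**3. Type I error if practices differ in change.** Let rho be the ICC of change (assumed; not in the documents) and m = 36 completers per practice (section D). The true variance exceeds the modelled one by DE = 1 + 35*rho, and type I error = 2*[1 - Phi(1.96/sqrt(DE))].

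| rho | DE | 1.96/sqrt(DE) | Type I error | Simulated |
|---|---|---|---|---|
| 0 | 1.00 | 1.960 | 5.0% | 5.1% |
| 1% | 1.35 | 1.687 | 9.2% | 9.3% |
| 3% | 2.05 | 1.369 | 17.1% | 17.1% |
| 5% | 2.75 | 1.182 | 23.7% | 23.4% |

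The simulation used 11 practices per arm and 20,000 trials. A t-test on practice mean changes held 4.9-5.2% in the same data.

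**4. If the table's ICC is an ICC of scores.** Then rho = ICC*(1-rc) / [ICC*(1-rc) + (1-ICC)*(1-rp)], with rc and rp the practice and patient autocorrelations (both assumed). Example: ICC 3%, rc 0.9, rp 0.5 gives 0.003/0.488 = 0.6%, DE 1.215 and type I error 7.5%. Over ICC 3-5% and rp 0.5-0.7, the error is 5% at rc = 1.0, about 6-9% at 0.95, 8-18% at 0.8-0.9 and 17-32% at 0.5.

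**5. Degrees of freedom alone do not repair it.** Referring the printed statistic to 18 df (20 practices, 44 each) still gave 16.8% at rho 3% and 24.0% at 5%.

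**6. Group terms.** A group intercept also cancels from change when patients stay in one cohort. If a group-by-time term replaced the practice term (simulated, 11 practices per arm), errors at a practice ICC of change of 1%, 3% and 5% were about 8%, 14% and 18% with five groups of seven and no group variance. They were about 8%, 12% and 14% with group variance twice the practice variance. Eight smaller groups push the upper end to about 15% and 20%. Overall this is roughly 7-8%, 12-15% and 14-20%.

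**The case against.** **Other provisions.** The equation is introduced as a basic model, and diagnostics will be used "to evaluate alternative model specifications". But no rule is set, and no omitted random term is named. A change-score analysis with a practice random effect would capture the missing variance, and given the general commitment to hierarchical models that is a natural reading. It would make a discrepancy visible, but it is a sensitivity analysis and does not make the primary test valid. The random-coefficient growth models are written for hypothesis II, with the level of the slope unstated. In the heterogeneity section, "we will examine variability between SMA groups separately for standard and patient-driven arms" does not alter the primary test.

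**A reader might infer that a practice slope was plainly intended.** Support could be sought in "In the model above we use practice level random effects" (plural) and in the C.4.1 phrase "using general linear mixed models with random slopes and intercepts". Neither carries much weight. The paragraph with the plural goes on to speak of one practice and one group effect, and the C.4.1 phrase belongs to a separate benchmark of 67 per group with no level given. What remains is the word bivariate, in a sentence that also mislabels the patient effect, so loose notation is a live explanation. The documents do not settle which reading is right.

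**Size.** It is fairly objected that the harm is unquantified: the calculations above run from none to severe. That stands, and it limits the claim to a missing term with conditional consequences.

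**Conclusion.** The point holds. As printed, the primary test omits practice-to-practice variation in change, and the equation conflicts with the sentence beneath it and with the clustering allowance in the power table. No other provision commits to a practice-by-time term.

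The size rests on an assumed ICC of change: no inflation at zero, about 9% at 1%, 17% at 3% and 24% at 5%, with 36 completers per practice and near-complete pairs. A reader might take the table's 3-5% as the ICC of change and conclude that the true error rate is 17-24%. The documents do not support that, because they do not say which scale the ICC is on. The group-replacement figures are likewise a range that depends on assumed group variance and number of groups.

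**What to change.** - Reconcile equation and text: write a practice-level random time effect (u_10j x time) into the primary model and correct the r_0ij / r_tij label.
- If groups are modelled, add group x time to the practice terms. Do not let it replace them on model fit.
- Test gamma_110 with practice-based degrees of freedom (2*10 - 2 = 18 to 2*11 - 2 = 20). Kenward-Roger is one option.
- State in advance what is done if the slope variance is estimated at zero. Either choice protects type I error: with no practice variation in change, simulated error was 2.9% keeping 20 df and 3.6% reverting to patient-level df. The rule matters for pre-specification, not validity.
- Keep a practice random effect in the change-score sensitivity analysis.
- State whether the power table's ICC and effect size refer to scores or to change. The hypothesised 0.30 is 0.60/2.0, standardised by a follow-up SD.

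**Cost.** SAP wording, one random term and a df option. Standard errors widen when practices differ in change, and the test is somewhat conservative when they do not. On the table's own formula, 18 df gives about 77% power at the four main-row effects (76.9%, 76.7%, 77.0%, 77.3%) instead of 81-82%.

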|---|--------------------------|--------------------------|-----|-----------------------|-------------------------------------|-------|
| 10 | 53.4 (534 per arm) | 44.5 (445 per arm) | 3% | 193 | .29 | >80% |
| 10 | 53.4 (534 per arm) | 44.5 (445 per arm) | 5% | 140 | .34 | >80% |
| 10 | 46.2 (462 per arm) | 38.5 (385 per arm) | 3% | 181 | .30 | >80% |
| 10 | 46.2 (462 per arm) | 38.25 (385 per arm) | 5% | 134 | .35 | >80% |
| For subgroup analyses (for patient characteristics) | | | | | | |
| 10 | 11.5 (115 per arm) | 9.6 (96 per arm) | 3% | 76 | .46 | >80% |
| 10 | 11.5 (115 per arm) | 9.6 (96 per arm) | 5% | 67 | .49 | >80% |

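### The power table uses large-sample quantiles for 20 randomised practices, so its main rows give about 77% rather than above 80%; it also leaves the SMA-group level unstated, with an effect that could go either way

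*Combined protocol and SAP*

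**What the plan says.** Section C.4.1 (Sample Size and Power Calculations) gives detectable effects of roughly .29 to .35 "for intent-to-treat analyses of primary outcomes with a type-1 error rate of .05". It separates the expected trial from the one used for power. The expectation is "We are expecting N (total) = 22 clinics, 1,000 patients (11 clinics and 500 patients" per condition, "allowing for ~15-20% attrition (leaving 400 patients per arm". For power, however: "However, we are estimating power based on 20 practices and provide a possible range of potential power to detect main effects".

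Each table row lists practices per arm, patients per practice before and after attrition, one ICC, an effective sample size, an effect size and a power. One main row reads "46.2 (462 per arm) | 38.5 (385 per arm) | 3% | 181 | .30 | >80" percent. No degrees of freedom, group-level ICC or baseline correlation is given.

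The same section describes treatment at each practice in around "8 cohorts of 8 to 10 patients each". Section C4.4.2d.1 (Quantitative analysis plan) writes the primary model with a practice random effect and then adds that "it is possible that groups (within practices) are a greater source of variation than practices per se". Variance components for groups within practices will be estimated, and both random effects kept if variability is sufficient. Section C.4.1 (Hypothesized Effect Size) sets the target at 0.30 and regards anything smaller as not clinically significant.

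**The concern.** Two features of the table looked optimistic. First, the comparison is between practices, and 20 practices give few degrees of freedom. Normal quantiles, or a t-test on patient-level degrees of freedom, understate the critical value. Second, patients are treated in groups within practices. The analysis plan provides for that level and the power table does not.

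The margin is thin. The rows at ICC 3% are stated to reach just above 80% at .29 and .30, and 0.30 is the plan's own threshold of interest. A few points lost at that effect would matter when a null result is interpreted, and the section on the importance of the knowledge to be gained treats a finding of no difference as informative.

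**Working it through.** **Inputs.** From the C.4.1 table: k = 10 practices per arm; m = 44.5 or 38.5 analysed patients per practice (9.6 in the subgroup rows); ICC 3% or 5%. One row prints 38.25 beside 385 per arm; 38.5 is used. From C4.4.2d.1: "Hypothesis tests will be two-sided with $\alpha = .05$ or p values reported".

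**Step 1: reproduce the table.** Design effect DE = 1 + (m − 1) × ICC. Effective N per arm E = 10m / DE. Detectable effect = (1.960 + 0.842) × √(2/E). For the first row, DE = 1 + 43.5 × 0.03 = 2.305, E = 445/2.305 = 193.1, and the detectable effect is 2.802 × √(2/193.1) = .285.

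Across the six rows E = 193.1, 140.2, 181.2, 133.9, 76.3 and 67.1, against 193, 140, 181, 134, 76 and 67 printed. The detectable effects are .285, .335, .294, .342, .453 and .484, which round up to the printed values. Normal-theory power at the printed effects is 81.0-81.7%. A t-test on patient-level degrees of freedom also fits (80.5-81.4%). A t-test on 18 df does not.

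**Step 2: cluster-level degrees of freedom, 20 practices.** Use the non-central t with 20 − 2 = 18 df, non-centrality d × √(E/2), and the same E.

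| Row (m, ICC) | Stated effect | Power, normal | Power, 18 df | 80% detectable effect, 18 df |
|---|---|---|---|---|
| 44.5, 3% | .29 | 81.3% | 76.9% | .302 |
| 44.5, 5% | .34 | 81.2% | 76.8% | .354 |
| 38.5, 3% | .30 | 81.5% | 77.0% | .311 |
| 38.5, 5% | .35 | 81.7% | 77.3% | .362 |
| 9.6, 3% (subgroup) | .46 | 81.1% | 76.6% | .480 |
| 9.6, 5% (subgroup) | .49 | 81.0% | 76.6% | .511 |

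**Step 3: the expected 22 practices.** Take 11 per arm, 20 df, and 400 completers per arm (20% attrition) or 425 (15%), so m = 36.4 or 38.6. Then E = 194.1 or 199.6 at ICC 3%, and 144.5 or 147.5 at ICC 5%.

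- ICC 3%: power is 80.3-81.3% at .30 and 77.6-78.7% at .29.
- ICC 5%: power is 80.8-81.6% at .35 and 78.5-79.3% at .34.

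**Step 4: the SMA group.** With g analysed patients per group, DE = 1 + (m − 1) × practice ICC + (g − 1) × group component. The documents give no group component, so both directions are shown for 20 practices, 18 df and g = 8 (assumed).

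- *Added to the stated ICC, and assumed equal to it.* First row: DE = 2.305 + 7 × 0.03 = 2.515 and E = 176.9. Over the four main rows E = 176.9, 126.2, 164.9 and 119.4, and power is 73.2%, 72.4%, 73.1% and 72.5%.
- *Carved out of the stated ICC, half at each level.* First row: DE = 1 + 43.5 × 0.015 + 7 × 0.015 = 1.7575 and E = 253.2. Power over the four main rows is 86-89%. Moving variance from a cluster of about 40 to one of 8 shrinks the design effect.

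**Step 5: baseline correlation.** The table takes no credit or penalty for it. With 20 practices, 18 df and no group component, an outcome variance 10% lower gives about 81% in the main rows; 20% higher gives about 69%.

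**The case against.** The strongest reply is that the table is a deliberately cautious grid. It is computed for 20 practices while 22 are expected, and it is presented as a possible range. This largely stands for the size of the problem: with 22 practices the shortfall disappears at .30 (ICC 3%) and at .35 (ICC 5%). It does not rescue the printed rows, which are labelled 10 practices per arm, and 1-2 points are still missing at .29 and .34.

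A second reply is that the formula is not the planned test. The primary analysis tests arm × time on repeated measures, and baseline distress is listed among the covariates. A modest gain from baseline information would restore 80%. This also stands, but in both directions: an unadjusted change contrast with low baseline correlation loses power. Moreover, the practice random intercept in the written model cancels from the arm × time term. What governs that test is variation in change between practices and between groups, and the table gives neither.

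A reader might go further and infer that treatment in groups means the stated power is not delivered, or that the plan expects groups to vary more than practices. The documents do not support either reading. The analysis plan calls greater group variation only possible, gives no value, and does not say whether the 3-5% ICC is practice-only or total. The 72-73% figure holds only if a group component equal to the practice ICC is added on top of it. The opposite assumption gives 86-89%. The analysis itself also allows for groups, so validity is not in question.

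**Conclusion.** The concern holds in a limited form. On the table's own inputs, with 20 practices and a between-practice test, power is overstated by about 4-5 points: about 77% in every row, with 80% detectable effects larger by .01 to .02 in the main rows and by about .02 in the subgroup rows. This needs no assumed group ICC. It rests on 18 df, equal practice sizes, and the table's own variance with no baseline adjustment. For the 22 practices expected, power is about 80-82% at .30 (ICC 3%) and .35 (ICC 5%), and 78-79% at .29 and .34.

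Omitting the SMA group is a gap in the planning assumptions. It is not a demonstrated loss of power, since its sign depends on what the 3-5% ICC represents. The net effect of baseline correlation is likewise unknown.

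**What to change.** In section C.4.1:

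1. Rerun the table with t quantiles on practices minus 2 degrees of freedom, for both 20 and 22 practices, and restate either the detectable effects or the power. Name the degrees-of-freedom method for the mixed models in C4.4.2d.1 so that the two agree.
2. Say whether the 3-5% ICC is practice-only or total.
3. Show a sensitivity range for the group component, both added to that ICC and carved out of it.
4. State the assumed baseline correlation, and base the calculation on the variance relevant to the arm × time test.

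The cost is recalculation and text. No patients or practices are added. For the 20-practice rows the stated power becomes slightly less favourable.

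### The random-effects rule lets model fit remove practice, the randomised unit, in favour of SMA group, and the printed hypothesis I model has no practice-by-time effect to protect its test

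*Combined protocol and SAP*

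**What the plan says.** Section C.4.1 (Study Design) states that "randomization will be clustered at the practice level using covariate constrained randomization". The power table in the same section uses practice as the cluster, with ICCs of 3% and 5%.

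The Quantitative analysis plan in C4.4.2d.1 prints the hypothesis I model. It has one scalar random effect for practice, one for patient and a residual, and the intervention effect is the arm-by-time coefficient γ110. The text under the equation calls the practice effect's distribution bivariate, which would imply a second practice effect such as a slope, but the equation contains none. Change scores adjusted for baseline are planned as sensitivity analyses.

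The plan then says that groups may vary more than practices, and continues: "we will estimate variance components for groups within practices and retain both random effects if there is sufficient variability". If both cannot be kept, "we will test each separately and examine model fit and variance components to determine which to retain". It gives no threshold for sufficient variability, does not say that practice must stay, and names no degrees-of-freedom method. Hypothesis II follows a similar approach with growth-curve models. Hypothesis III names a practice random effect with no alternative.

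**The concern.** In a cluster-randomised trial, the arm comparison has to be judged against variation between the randomised units. A practice variance that looks small or non-significant with 20 or 22 practices is poorly estimated; that is not evidence that it is zero. If practice is dropped and group kept, the groups act as independent replicates of the arm although only 22 units were randomised. The error term is then chosen from the outcome data, and any contrast that carries practice variation gets a standard error that is too small. The rule also contradicts the power table, which takes the practice ICC to be above zero.

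**Working it through.** **1. The plan's own figures.** Effective n per arm = n / [1 + (m − 1) × ICC], with m the completers per practice:

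- 445 / (1 + 43.5 × .03) = 193; at ICC .05, 140
- 385 / (1 + 37.5 × .03) = 181; at ICC .05, 134
- 96 / (1 + 8.6 × .03) = 76; at ICC .05, 67

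All six match the table. Power at the stated effect sizes is 81-82%, in line with the stated >80%. The sizing therefore does rest on practice clustering.

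**2. A contrast that carries practice variation** (change score or single follow-up score). Assumed layout: 22 practices, 5 groups each, 7 completers per group, total variance 1, group ICC .03. The documents give no group ICC. Five groups is inferred from about 45 patients per practice in groups of 8-10; C.4.1 itself speaks of around 8 cohorts.

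Expected mean squares: group = residual + 7 × group ICC; practice = group mean square + 35 × practice ICC. A group-only model pools practices (20 df) with groups within practices (88 df) into 108 df.

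| Practice ICC | Residual | Group MS | Practice MS | Pooled MS | SE ratio |
|---|---|---|---|---|---|
| .02 | .95 | 1.16 | 1.86 | (20 × 1.86 + 88 × 1.16)/108 = 1.29 | √(1.29/1.86) = .83 |
| .05 | .92 | 1.13 | 2.88 | (20 × 2.88 + 88 × 1.13)/108 = 1.45 | √(1.45/2.88) = .71 |

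The group-only standard error is 17% and 29% too small.

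**3. How often the rule would do this.** Simulation of the rule for such a contrast: 40,000 runs per setting, 20 practices, 5 groups of 8, practice ICC .01-.05, group ICC assumed between 0 and .08.

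| Reading of the rule | Group-only chosen | Type I error in those trials | Overall type I error |
|---|---|---|---|
| An effect is dropped only when its variance estimate is zero | 0.3-27% | 8-23% | 4.4-5.1% |
| Both effects must be significant to be kept | 18-75% | 8-18% | 5.5-7.4% |
| Practice always kept | never | not applicable | about 5% |

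**4. The printed hypothesis I test.** A practice or group intercept is the same at both visits, so it cancels from the arm-by-time contrast. Generalised least squares check with 22 practices, 5 groups of 9, 18% missing follow-up, practice and group variances .03, patient variance .5 and residual .45 (all variances assumed): the SE of γ110 is 0.0649 with practice only, group only or both. Only the baseline arm term changes, from about 0.10 with practice to 0.078 with group only, and that term is not the hypothesis test.

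**5. What does affect that test.** Suppose practices differ in their change over time with variance v. With 11 practices per arm and about 37 completers each (45 × .82), the true SE of γ110 is approximately √{(2/11) × [v + 2 × .45/36.9]}:

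- v = 0: √(.1818 × .0244) = 0.067
- v = .02: √(.1818 × .0444) = 0.090
- v = .05: √(.1818 × .0744) = 0.116

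The least-squares calculation, which also uses patients without follow-up, gives a reported SE of about 0.065 against a true 0.089-0.116 over the same range. The practice intercept was retained throughout, so retaining it does not close the gap.

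**The case against.** A reader might infer that dropping practice shrinks the standard error of the primary DDS-17 test and moves it from 20 to 108 degrees of freedom. The documents do not support that for the model as printed: γ110 has neither a practice nor a group component, and step 4 shows that its standard error does not move. The inference would hold only if the word bivariate stands for a practice slope that the equation leaves out, and the plan does not say so.

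Nor does the rule reach every model. Hypothesis III already names a practice effect, and hypothesis IV uses staff surveys, in which patient groups are not a level. Change scores are sensitivity analyses. The group-only model is a fallback, and under the narrowest reading overall type I error stays near 5%. The group ICC and the number of groups are assumptions.

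All of this stands, and it limits the size of the problem. It does not justify leaving the rule as it is. The rule still permits the randomised unit to be removed on fit. A trial that ends in the group-only branch would report a test that rejects well above 5% of the time under no effect, where practice variation enters the contrast. Keeping only the practice intercept would also leave the primary test unprotected.

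**Conclusion.** The concern holds in limited form. The rule conflicts with practice-level randomisation and with the plan's own power table. For contrasts that carry practice variation, the group-only model's standard error is about 17% too small at practice ICC .02 and 29% at .05, under the assumed layout and group ICC. Overall type I error is between about 5% and 7%, depending on a threshold that the plan leaves undefined.

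The primary γ110 test is untouched by the choice between intercepts. Its exposure comes from the absent practice-by-time effect, and its size depends on a variance that the documents do not give. If that variance is zero, the reported standard error is right; at .02-.05 it is roughly 0.73 to 0.56 of the true value (0.065/0.089 and 0.065/0.116).

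**What to change.** Replace the retention rule in C4.4.2d.1 with text to this effect:

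*Practice is retained in every patient-level arm comparison regardless of its estimate or model fit. For γ110 and the growth-curve models, a practice-by-time random effect is included (or follow-up or change, adjusted for baseline, is analysed with a practice effect). Group within practice is added when estimable and never replaces practice. The arm contrast uses between-practice degrees of freedom (20 with 22 practices, 18 with 20).*

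The hypothesis I equation and the description of the practice effect as bivariate should be brought into line with this. Group-only models can still be shown descriptively.

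The cost is a few sentences, with no change to design or data collection. Confidence intervals will be slightly wider when practice variation is small, and wider by the amount that the design requires when it is not.
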